14.1 Sample Size

In the absence of predefined hypotheses, the desired sample size is based on the precision of estimates and half-widths of confidence intervals. The target enrollment cohort of 70 to 100 will provide between 60 and 85 evaluable subjects at month 12 [REDACTED]

Table 3 Sample Size Calculations

14.2 Statistical Analysis

[REDACTED]

[REDACTED] Results will be compared to competitive products from the available literature.

The primary analyses will include all subjects enrolled and followed. Additional analyses will be conducted where results are tabulated separately for subjects who require a revision procedure in one or both compartments and receive a product other than Axis Dermis and those who do not receive any additional product other than Axis Dermis during study follow-up.

15 Data Quality Assurance

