Enterocoele: When the small intestine drops and protrudes into the vagina. This usually occurs in conjunction with one or more of the other types of prolapse listed above.

Depending on the severity and stage of prolapse, many women do not need treatment. Some women find that their symptoms are relieved through special pelvic muscle exercises call Kegel Exercises, which are used to strengthen the muscles that surround the opening of the urethra, vagina, and rectum. Making dietary changes, maintaining a healthy weight, not smoking, and avoiding heavy lifting and straining also help to relieve symptoms. Medication is available to help treat urinary and bowel symptoms of POP. Further, a device called a pessary can be inserted into the vagina to support the pelvic organs. For women who can be fitted properly and whose pelvic organ support can be maintained with a pessary, this form of treatment has a high probability of success.

[REDACTED]

[REDACTED]

3 Product Description

Coloplast's Axis™ Allograft Dermis consists of [REDACTED], preserved human collagen. [REDACTED]

4 Study Purpose and Design

This study is a prospective, single arm, multi-center, post-market study to evaluate the efficacy of Axis™ Allograft Dermis used for anterior, posterior or combined (anterior and posterior) pelvic organ prolapse repair. Target enrollment is 70-100 subjects enrolled at 5 to 10 investigational sites in the United States. [REDACTED]

5 Objectives

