5.1 Primary Objective

The primary objective of this study is to evaluate efficacy of the Axis Dermis graft used for soft tissue repair, replacement, reconstruction, or augmentations in the correction of POP as assessed by POP-Q Stage improvement based upon an objective grading of prolapse of the anterior, posterior or combined anterior and posterior (assessed individually) compartment(s) compared between baseline and one year. Grading of the prolapse will be categorized as follows:

Cured: POP-Q Stage reduced to 0 or 1, or improved by 2 stages from baseline

Improved: POP-Q Stage > 1, but improved by 1 stage from baseline

Failed: POP-Q Stage stayed the same or increased in severity from baseline

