6.3 Inclusion Criteria

Patients must meet all of the following criteria to be included in the study:

1. Adult female at least 18 years of age.
2. Willing and able to provide written informed consent.
3. Confirmed pelvic organ prolapse (POP) of Stage 2 or higher as determined by POP-Q prolapse grading requiring surgical intervention in the anterior, posterior or combined (anterior and posterior) compartment.
4. Willing and able to complete all follow-up visits and procedures indicated in this protocol.

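### Section 14.2 compares Axis with published results for competing products, and no visible text requires the success definitions to be matched

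*Combined protocol and SAP*

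**What the plan says.** - **Design (Section 4).** "This study is a prospective, single arm, multi-center, post-market study to evaluate the efficacy of Axis". There is no concurrent control.
- **Sizing (Section 14.1).** "In the absence of predefined hypotheses, the desired sample size is based on the precision of estimates and half-widths of confidence intervals". Then: "The target enrollment cohort of 70 to 100 will provide between 60 and 85 evaluable subjects at month 12". No margin, benchmark or performance goal is visible.
- **External comparison (Section 14.2).** "Results will be compared to competitive products from the available literature". The text immediately before this sentence is redacted. The visible part names no comparator, no search or selection rule, no date for fixing the choice, and no step that puts published outcomes and Axis outcomes on one definition.
- **Outcome (Section 5.1).** "Cured: POP-Q Stage reduced to 0 or 1, or improved by 2 stages from baseline". Where both compartments are repaired, each is graded on its own.
- **Entry (Section 6.3).** "Confirmed pelvic organ prolapse (POP) of Stage 2 or higher as determined by POP-Q prolapse grading". Stage 4 is therefore eligible. No expected stage mix is given.
- **Revision.** Under Section 14.2, the primary analyses take in everyone enrolled and followed. Women revised with a product other than Axis are split out only in additional tabulations. Section 5.2 lists the revision rate of the index prolapse as a separate secondary outcome, and Section 8.6 has every revision recorded on a form. No visible sentence says how a revision enters the cure, improved or failed grading.

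**The concern.** With one arm and no hypothesis, any statement about Axis relative to another product has to come from this literature comparison. A published success rate is tied to its own rule: which stages count, whether the unit is a woman or a compartment, when it is measured, and what happens to women who are reoperated. The Axis rate has its own answers to these questions, and the visible plan does not ask that they be aligned.

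Two of the Axis features can only raise the rate relative to a stricter rule: the two-stage clause, and keeping revised women without counting revision as failure. If the comparator uses a stricter rule, part of the gap between the two rates would come from definition and not from the product, and a reader could not tell how much.

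**Working it through.** **1. The plan's own figure.** 60/70 = 85.7% and 85/100 = 85.0%, so the evaluable numbers imply losses of 14.3% and 15.0%. They agree with a loss of about 15%. That rate is back-solved, since no attrition rate is visible.

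**2. What the two-stage clause adds.** I compared every pair of baseline stage (1 to 4) and 1-year stage (0 to 4) under the plan's rule and under a plain Stage 0 or 1 rule. They differ in exactly one pair: baseline Stage 4, 1-year Stage 2. From Stage 2 or 3, a two-stage gain already ends at Stage 0 or 1. Hence

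gain = (share at Stage 4) × P(Stage 4 ends at Stage 2).

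Both inputs are assumptions:
- 5% × 20% = 1 point
- 15% × 40% = 6 points
- wider ranges: 2% × 10% = 0.2 points, and 20% × 50% = 10 points

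The share refers to whatever unit is graded, woman or compartment.

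**3. What revision handling can add.** The documents give no expected revision rate, so only the step size can be shown. Counted per woman, each woman who is revised and then graded cured adds 1/60 = 1.7 points or 1/85 = 1.2 points over a rule that counts revision as failure.

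**4. Unit.** A per-compartment rate need not equal a per-woman rate. The direction depends on how failures cluster in women with combined repairs, and the documents give nothing from which to size it.

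**5. Sampling error.** Assume Axis 80% and a published 70% of 100, a difference of 10 points. The 95% half-width is

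1.96 × √(0.80 × 0.20/n + 0.70 × 0.30/100).

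- n = 60: 1.96 × √(0.16/60 + 0.21/100) = 13.5 points
- n = 85: 1.96 × √(0.16/85 + 0.21/100) = 12.4 points

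Both exceed 10 points. For the Axis rate alone at 80%, the half-width is 10.1 points (n = 60) or 8.5 points (n = 85).

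**6. Choice of comparator, only if it is left open.** This is an illustration with 100,000 simulated runs per setting. All products have a true rate of 80%, each published series has 80 women, and the lowest of k series is taken as comparator. The mean apparent Axis advantage is 0 points for k = 1, 3.8 for k = 3, 5.3 for k = 5 and 7.1 for k = 10. The chance that a pooled z exceeds 1.96 in favour of Axis rises from about 2.5% (k = 1) to 12.3% (n = 60) or 13.8% (n = 85) at k = 10.

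**The case against.** The strongest reply is that the sentence in Section 14.2 prescribes no paper, definition, test or claim. A comparison with papers chosen in advance and definitions matched would comply with it. The word used is results, which also covers stage change, revision rate, questionnaires and adverse events, so use of the composite cure rate is an inference. The plan says "In the absence of predefined hypotheses" and shows no superiority or equivalence aim. Revision is reported as its own outcome, and women revised with another product are tabulated separately. The sizes above rest on assumed stage mixes and comparators, and the sampling error is symmetric: it can hurt Axis as easily as help it.

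Much of this stands, and it rules out some stronger readings that a reader might infer:

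- *That comparators can be picked once the results are known.* The documents do not establish this. Redacted text directly precedes the sentence and may fix them. It can only be said that the visible text fixes none.
- *That the comparison favours Axis by construction.* The two-stage clause matters only for Stage 4 to Stage 2. Its effect is nil if no one makes that change or if the comparator has the same clause, and the bias reverses if the comparator's rule is looser. No visible text says which rules the published series use.
- *That this is the study's only comparison.* The primary objective has stage in the repaired "compartment(s) compared between baseline and one year", and secondary objectives assess change from baseline. It is the only visible comparison with other products.
- *That the sentence, followed exactly, must give an unsound result.* It need not; it permits a sound comparison as well as an unsound one.

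The reply does not remove the mismatch. The cure definition, the grading by compartment and the analysis-set sentence are all unredacted, and none of them is tied to the definition a comparator uses. Separate tabulation of revised women helps, but it does not give a rate with revision counted as failure.

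**Conclusion.** The point holds in a limited form. The visible plan commits to a comparison with competing products without requiring matched definitions, and the Axis cure rate can exceed a rate based on Stage 0 or 1 only or on reoperation as failure. The two-stage clause is worth 1 to 6 points if 5% to 15% are at Stage 4 and 20% to 40% of those end at Stage 2. Revision handling adds 1.2 to 1.7 points per woman concerned, and the effect of the unit cannot be sized. Sampling error of about ±12 to 14 points around a 10-point difference is separate from this bias, but it means that a gap of that size would not by itself distinguish the products. The stage mix, transition rate, Axis rate and comparator are all assumptions. The direction of bias depends on definitions that the documents do not show. This is a cheap improvement to the plan; it does not invalidate the study.

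**What to change.** In Section 14.2:

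1. For each comparator publication, recompute the Axis rate with that paper's success definition, unit (woman or compartment), time point and handling of reoperation, using the POP-Q stages and Revision Forms already collected.
2. Beside the composite cure rate, report a Stage 0 or 1 rate with revision counted as failure.
3. Show the rates with 95% intervals and give the baseline stage mix.
4. Unless the redacted text already does so, fix the comparator publications or the rule for selecting them before the 1-year analysis, and label the comparison descriptive, supporting no claim of superiority or equivalence. If the redacted text covers this, confirmation is enough.

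The cost is about a page of plan text and some re-tabulation, with no new visits, measurements or participants. The downside is that the Axis rate may look less favourable under stricter definitions.

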AXIS Protocol

Cover Page

NCT01541748

**Axis Allograft Dermis for female Pelvic Floor Repair: a Prospective Post Market
Study**

Most recent version 24Oct2011

Axis™ Allograft Dermis for Female Pelvic Floor Repair: a Prospective Post Market Study

Clinical Investigational Plan (CIP)

Investigational Plan #: CP009SU

This confidential document is the property of Coloplast Corp. No unpublished information contained herein may be disclosed without written approval of Coloplast Corp.

Signature page

SPONSOR	INVESTIGATOR
Coloplast Corp. [name] USA [contact]	Name Address Postal code and city Country Telephone number:
APPROVER	
	Name and title of the Investigator
Date	Date
Date	
Date	

Table of Contents

Signature page 2

1 Protocol Summary 4

2 Background 4

3 Product Description 6

4 Study Purpose and Design 6

5 Objectives 6

6 Study Population 7

7 Enrollment 7

8 Procedures 8

9 Study Product 10

10 Protocol Deviations 11

11 Adverse Events 11

12 Withdrawal / Study Exit 13

13 Electronic Case Report Forms (eCRFs) 13

14 Statistical Methods 13

15 Data Quality Assurance 14

16 Regulations and Guidances 15

17 Publication 16

18 Records and Retention 16

19 [REDACTED] 18

Appendix A: [REDACTED] 20

Attachment 1: [REDACTED] 22

Appendix B: Patient Questionnaires 24

1 Protocol Summary

Title	Axis™ Allograft Dermis for female pelvic organ prolapse repair: a post market study
Sponsor	Coloplast Corp. [name]
Product	Axis Allograft Dermis
Study Design	A prospective, single arm, multi-center, post market study of the efficacy of Axis™ Allograft Dermis for anterior, posterior or combined female pelvic floor repair.
Primary Objective	POP-Q Stage improvement from baseline at 1 year post operatively, categorized as cure, improved or failed.
Secondary Objective	POP-Q Stage at 6 weeks, 6 months, 2 year, and 3 year follow-up 

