5.2 Secondary Objectives

Secondary objectives will assess POP-Q Stage and patient satisfaction at 6 weeks, 6 months, 2 years, and 3 years post implant, as follows:

Change in prolapse stage from baseline as determined objectively by POP-Q prolapse grading at 6 weeks, 6 months, 2 year, and 3 year follow-ups. Change in patient satisfaction from baseline and quality of life measured through validated questionnaires (PDFI-20 and PFIQ-7)⁶

Change in patient sexual satisfaction from baseline measured through a validated questionnaire (PISQ-12)⁷

Summary of Patient Global Impression of Improvement (PGI-I) for urogenital prolapse⁹ results

Summary of The Institute for Female Pelvic Medicine & Reconstructive Surgery Surgical Satisfaction Questionnaire (SSQ-8) results¹⁰

Change in Pelvic and Sexual Health Institute Visual Analog Scale (VAS)¹¹ results

Surgical revision rate of the index prolapse(s)

Summary of all mild, moderate, and serious product and/or procedure related adverse events

6 Study Population

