8.4 Follow-Up Schedule

Follow-up visits are required at 6 weeks, 6 months, 1 year, 2 years, and 3 years post implant. If the participant misses any required follow-ups, a Study Deviation Form must be completed. Every attempt should be made to complete the visit, however, if the subject cannot be seen in person the required questionnaires should be mailed to the participant with a postage paid return envelope. If a scheduled visit is not within the follow-up window, the visit should still be completed as soon as possible and a Study Deviation Form completed.

Table 2 Follow-up Schedule & Visit Windows

Follow-Up	Window Start	Target Day	Window End
[REDACTED]	[REDACTED]	[REDACTED]	[REDACTED]
[REDACTED]	[REDACTED]	[REDACTED]	[REDACTED]
[REDACTED] [REDACTED]	[REDACTED]	[REDACTED]	[REDACTED]
[REDACTED] [REDACTED]	[REDACTED]	[REDACTED]	[REDACTED]

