8.5 Follow-Up Visits

8.6 Revision Procedure

If during the follow up period a subject requires urogynecological surgery (i.e. additional or revision POP repair, mid-urethral sling, hysterectomy, etc.), complete the Revision Form. If a revision procedure is performed as the result of an adverse event (e.g. infection, rejection, pain), complete the Adverse Event form in addition to the Revision form.

9 Study Product

All investigative sites will be required to maintain an adequate stock of Axis Dermis. The lot number and size of each product used will be recorded on the Procedure Form.

10 Protocol Deviations

A protocol deviation is defined as an event where the clinical investigator or site personnel did not conduct the study according to the clinical investigational plan or the investigator agreement. All protocol deviations must be documented on a Study Deviation Case Report Form.

Reporting of protocol deviations should comply with local IRB policies and/or local laws.

11 Adverse Events

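### The additional tabulation in 14.2 groups women by product received at any time in follow-up, not by prolapse reoperation up to the visit, so its no-other-product result is not the 1-year result of the index Axis repair

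*Combined protocol and SAP*

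**What the plan says.** The Protocol Summary gives the primary endpoint as "POP-Q Stage improvement from baseline at 1 year post operatively, categorized as cure, improved or failed". Section 5.1 defines the three categories by stage alone. The last one reads "Failed: POP-Q Stage stayed the same or increased in severity from baseline", and reoperation appears in none of them.

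Section 14.2 fixes the main analysis set: "The primary analyses will include all subjects enrolled and followed". It then adds a tabulation of two groups:

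- "subjects who require a revision procedure in one or both compartments and receive a product other than Axis Dermis" (below, the other-product group);
- "those who do not receive any additional product other than Axis Dermis during study follow-up" (below, the no-other-product group).

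These short labels are mine. Three other sections bear on how the rule works:

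- Section 8.4: "Follow-up visits are required at 6 weeks, 6 months, 1 year, 2 years, and 3 years post implant". Section 12, however, treats participation as complete after the two-year visit.
- Section 8.6 sends later urogynecological surgery to the Revision Form, with the examples "additional or revision POP repair, mid-urethral sling, hysterectomy, etc".
- Section 5.2 makes the surgical revision rate of the index prolapse a secondary endpoint, whatever material is used.

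**The concern.** The first group needs two conditions: a revision in a compartment, and a non-Axis product. The second needs one: no further non-Axis product. Reoperation is not part of the second definition, and neither definition is tied to the visit being analysed.

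This is a single-arm study without predefined hypotheses, and 14.2 says its results will be set against published results for competing products. In that setting the no-other-product row is easily read as how the Axis repair performs when nothing else intervenes. As defined, it can contain women whose Axis repair had to be redone. It can also lose women at 1 year because of something that happened in year 2 or 3. With 60 to 85 evaluable women, moving a few of them shifts the rate visibly.

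**Working it through.** **Size of the study.** Section 14.1 expects 60 to 85 evaluable women from 70 to 100 enrolled. The attrition rate is not visible, so it can only be back-solved: 1 − 60/70 = 14.3% and 1 − 85/100 = 15.0%. A single 15% gives 59.5 and 85.0. The figures are coherent, and 60 and 85 are used below.

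**Step 1: apply the two definitions.** Suture is taken not to be a product, and the compartments are taken to be anterior and posterior.

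| Event after the index repair | Group under 14.2 |
|---|---|
| No reoperation | No-other-product |
| Prolapse re-repair, sutures only | No-other-product |
| Prolapse re-repair, second Axis graft | No-other-product |
| Prolapse re-repair, other product, month 8 | Other-product |
| Prolapse re-repair, other product, month 30 | Other-product, including for the 1-year table |
| Mid-urethral sling only | Neither on this reading; see the objection |

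Rows 2 and 3 place reoperated women with never-reoperated women. Row 5 lets a later event decide membership at 1 year. It holds for any revision between 1 year and the end of follow-up, whether that end is the two-year or the three-year visit.

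**Step 2: direction, 85 women, assumed counts.** Suppose 75 women are not reoperated by 1 year, 70 of them cured. Another 10 are reoperated before 1 year, 4 with another product and 6 with sutures or Axis. The rate in women not reoperated by 1 year is 70/75 = 93.3%.

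*Reoperation scored as failure:*
- all subjects: 70/85 = 82.4%;
- no-other-product group, events to month 12 only: 70/(85 − 4) = 70/81 = 86.4%;
- as written, if 3 uncured women get another product later: 70/78 = 89.7%;
- as written, if 3 cured women get another product later: 67/78 = 85.9%.

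*Stage alone, all 10 second operations graded cured:*
- all subjects: 80/85 = 94.1%;
- no-other-product group, events to month 12 only: 76/81 = 93.8%;
- 3 uncured women leave later: 76/78 = 97.4%;
- 3 cured women leave later: 73/78 = 93.6%.

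Keeping the 6 re-repaired women in the group lowers its rate under the first scoring (86.4% against 93.3%) and raises it slightly under the second (93.8% against 93.3%). Under the first scoring, removing 3 late revisers moves 86.4% to 89.7% or to 85.9%, depending on their 1-year grade. The lowest first-scoring figure is 85.9 − 93.3 = −7.4 points from the non-reoperated rate.

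**Step 3: range over other assumed counts.** Here 1-year cure is 85% (rounded to whole women) in women not reoperated by month 12, late revisers apart, and suture or Axis re-repairs by month 12 are graded cured. The counts are, in order: early other-product revisions, early suture or Axis revisions, late other-product revisions (of which cured at 1 year), sling only. Low is 1, 1, 2 (1), 1; mid is 2, 2, 4 (1), 2; high is 3, 4, 8 (2), 4. Sling-only women are left out of the no-other-product group.

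| N | Case | No-other-product, as written | Not reoperated by month 12 | Same, if all late revisers were cured at 1 year |
|---|---|---|---|---|
| 60 | low | 48/56 = 85.7% | 49/58 = 84.5% | 50/58 = 86.2% |
| 60 | mid | 44/52 = 84.6% | 45/56 = 80.4% | 48/56 = 85.7% |
| 60 | high | 39/45 = 86.7% | 40/53 = 75.5% | 46/53 = 86.8% |
| 85 | low | 69/81 = 85.2% | 70/83 = 84.3% | 71/83 = 85.5% |
| 85 | mid | 66/77 = 85.7% | 67/81 = 82.7% | 70/81 = 86.4% |
| 85 | high | 60/70 = 85.7% | 61/78 = 78.2% | 67/78 = 85.9% |

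Against the fourth column the group as written is up to 86.7 − 75.5 = 11.2 points higher. Against the last column it is 0.1 to 1.1 points lower. The sign depends on counts and scoring that the documents do not give.

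**The case against.** The strongest defence is that the split answers a different and legitimate question: whether another product has contaminated the result. It is an additional descriptive tabulation. Both groups are shown, the primary analysis keeps everyone, and the revision rate is reported on its own. Parts of 14.2 just before this text, and the end of the efficacy statement in section 14, are redacted. Timing or scoring rules could be there.

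Much of this stands and limits the impact. It does not rescue the rule as visible. Even for contamination, only a product received before a visit can affect that visit's result, so sorting the 1-year table on the whole follow-up is wrong for that purpose too.

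Three stronger readings are tempting, and the documents do not support them:

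- *The no-other-product cure rate is too high by construction.* If reoperation is scored as failure, keeping suture and repeat-Axis re-repairs in the group lowers its rate. Removing late revisers raises the rate only if they did worse at 1 year than the rest of the group. Only those revised with a non-Axis product leave, so it is not true that later failures in general drop out.
- *A sling-only woman certainly falls in neither group.* That is one of three readings. Section 8.6 is headed as revision and covers slings, which could place her in the other-product group. Section 6.4 exempts slings from the bar on concurrent non-Axis treatment, which suggests that a product means a prolapse-repair product and would place her in the no-other-product group. What is established is that the terms are undefined and the two definitions are not complements.
- *The plan presents this group as the Axis-alone result.* It does not use such a label. The risk is in how readers will take the row.

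**Conclusion.** The concern holds as a fault in a stated rule that should be corrected. As visible, 14.2 sorts by non-Axis product at any time in follow-up. It leaves suture-only and repeat-Axis re-repairs with never-reoperated women, lets events after 1 year decide who counts at 1 year, and leaves sling-only women to undefined terms. The no-other-product figure is therefore not interpretable as the 1-year result of the index Axis repair.

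No size or direction can be derived from the documents. Under the assumed counts above, the figure lies between 7.4 points below and 11.2 points above the rate in women not reoperated by month 12. All reoperation counts and cure rates there are assumptions. The conclusion also assumes that suture is not a product and that no redacted text supplies a timing rule. The all-subjects primary analysis and the revision-rate endpoint are not changed by the split, so this is an important correction rather than a threat to the main result.

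**What to change.** Replace the split in 14.2 with a rule along these lines:

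> At each visit, subjects are classified using only events up to that visit: (a) no repeat prolapse surgery in an Axis-treated compartment; (b) repeat surgery there without a non-Axis product (sutures only or a second Axis graft); (c) repeat surgery there with a non-Axis product. Slings, hysterectomy and other urogynecological surgery are shown separately and do not change the group.

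Keep the all-subjects result, with reoperated women in the denominator, as the headline efficacy figure. State how their 1-year grade is scored, since the visible text does not. Label any rate in non-reoperated women as descriptive and selected. Reconcile the end of follow-up in section 12 with the schedule in 8.4, because the two give different meanings to study follow-up.

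The cost is a wording change and one derived variable from the Revision Form date and procedure. The groups become smaller, and the subgroup figure may move up or down: in the 85-woman example with reoperation scored as failure, group (a) would show 93.3% where the present rule shows 85.9% or 89.7%.
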